5. BACKGROUND AND RATIONALE

Intermittent fasting is a dietary regimen defined by alternating fasting and “feeding” cycles. In addition to caloric restriction (a dietary regimen limited to a daily food intake lower than one’s daily caloric needs) only, intermittent fasting seems to activate cell autophagy (cellular “recycling” program) which potentially increases cellular stress resistance and removes accumulated molecules that are potentially toxic¹⁻³. In fact, mice maintained on intermittent fasting without decreased overall food intake show effects on body weight reduction that equal and in some cases even exceed those of calorie restriction^{4, 5}. However, additionally, intermittent fasting combined with even a high-fat diet in the feeding periods protects mice from obesity, hyperinsulinemia, hepatic steatosis, and inflammation compared to controls that are fed an *ad libitum* high-fat diet despite the same calorie intake⁶, making this intermittent fasting regimen a promising approach to reduce morbidity and mortality in various species.

The best described and most widely practiced version of intermittent fasting is the “alternate day diet” or “alternate day fasting” (ADF). In animal models, ADF consists of an *ad libitum* “feed day” alternated with a 100% restriction “fast day”. However in humans, this is often modified to allow a small amount of food consumption on the “fast day” (e.g. 25% of the individual’s energy needs). Findings from recent modified ADF studies showed 4-8% reduction in body weight after 8-12 weeks⁷⁻¹⁰. This reduction in body weight is usually escorted by reductions in triglycerides^{8, 10, 11}, low density lipoprotein (LDL) cholesterol^{8, 10, 11}, systolic blood pressure¹⁰, insulin resistance⁷ and increases in LDL particle size^{7, 12, 13}.

However, knowledge about the molecular effects of the alternate day diet on human metabolism or autophagy is still scarce since detailed analyses of molecular and metabolic parameters remain unexplored, especially in healthy individuals. The overarching aim of this research project is to elucidate in which extent alternate day fasting (and thereby intermittent fasting) influences human physiology in healthy individuals in both short and long term. The secondary objective of this study is to define novel molecular markers of aging and age-related diseases.

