8. OUTCOMES

8.1 Primary outcome measures in the cohort study

- Differences in body composition (fat mass and lean body mass) between groups
- Differences in resting energy expenditure between groups
- Differences in insulin sensitivity (Matsuda Index, ISI, HOMA-Index, QUICKI) between groups
- Difference in glycaemic pattern (continuous glucose measurement) between the two groups
- Differences in endothelial function (Mean Intima media thickness, Reactive Hyperaemia Index, Stiffness Index, Aortic augmentation index) between groups
- Differences in mean 24h blood pressure between groups
- Differences in hormonal regulation (fertility, appetite hormones and others)

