10. SELECTION AND WITHDRAWAL OF STUDY SUBJECTS

10.1 Subject Selection

The study population will consist of 100 healthy subjects. Fifty participants of them should already practice Alternate Day Fasting. Subjects in the ADF and control group will at least be matched by sex, weight and age. Subjects of the control group will be asked to participate in a pilot randomized controlled trial. A separate informed consent will be used for the intervention study.

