11. STUDY PROCEDURES

11.1 Schedule of study procedures of the cohort study

	Visit 1	Visit 2 (9 ± 4 days after visit 1)
Informed Consent	X	
Inclusion/exclusion criteria	X	
Demography, medical history	X	

Concomitant medication	X	X
Vital signs	X	X
Physical examination	X	
Blood sampling (FMD)	X	X
Dual-energy X-ray absorptiometry (DXA)		X
Oral glucose tolerance test (OGTT)	X	X (ADF group only)
Electrocardiography (ECG)	X	
Questionnaires (FFQ, Physical Activity)		X
Retinal vessels analyser		X
Continuous Glucose monitoring (CGM)	X	
Hand-Grip Test		X
Accelerometer (Movisens®)	X	
Endothelial function (EndoPat 2000)		X
Intima media thickness (IMT)		X
Pulse wave analysis		X
Buccal mucosa sampling	X	
24h blood pressure measurement	X	
Sputum sampling	X	
Faeces sampling	X	
Echocardiography	X	
Resting energy expenditure (REE)		X
Bioelectrical impedance analysis (BIA)		X
Dry eye assessment (optional)		X
Flow mediated dilatation (FMD)		X

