12. METHODS

12.1 Oral glucose tolerance test (OGTT)

Various insulin sensitivity indices derived from a frequently sampled, extended oral glucose tolerance test (OGTT) will be calculated accounting for the various weighting of hepatic and peripheral insulin sensitivity expressed by the different indices. Insulin, C-peptide and glucose will be measured before and 15, 30, 60 and 120 minutes after ingestion of 75g glucose ([®]Glucoral 75 citron, Germania Pharmazeutika, Vienna). In addition, lipid-parameters (total cholesterol, triglycerides, HDL, LDL, free fatty acids) and a routine safety lab will be measured. The OGTT will be performed after an overnight fast (apart from water). A standard gauge cannula will be placed into a subcutaneous vein for blood sampling. In order to prevent blood clotting in the cannula and to keep the cannula working it will be occasionally flushed with sterile normal saline. A pre-meal blood sample will be taken (-5 mins) and then all subjects will be asked to drink the sugar solution over a period of 2-4 mins (time 0 min). During the OGTT further blood samples will be taken at 15, 30, 60, and 120 minutes. The blood at each time point will be placed into a fluoride oxalate tube (1ml) for plasma glucose and into a serum tube for analyses of insulin and c-peptide.

The insulin sensitivity index will be calculated from the OGTT according to four different equations: the

Matsuda-Index (IS_{OGTT}): $IS_{OGTT} = \frac{10000}{\sqrt{(glucose_0 * insulin_0) * (mean\ glucose * mean\ insulin)}}$,¹⁴ the HOMA-IR

(Homeostasis Model Assessment for Insulin Resistance): $HOMA - IR = \frac{FPG(\text{mmol/l}) * FSI(U/l)}{22.5}$ ¹⁵ and the

$QUICKI = \frac{1}{\log(insulin_0) + \log(glucose_0)}$ ¹⁶. The last equation was proposed by Stumvoll et al. (insulin

sensitivity index ISI): $ISI = 0.222 - 0.00333 * BMI - 0.0000779 * Ins_{120} - 0.000422 * age$ ¹⁷.

Beta-cell function will be estimated in the fasting state with $HOMA - \beta = \frac{20 * Insulin_0}{Glucose_0 - 3.5}$ ¹⁵ and during

the OGTT with the Stumvoll-Index: $1st\ phase = 1283 + 1.829 * Ins_{30} - 138.7 * Glc_{30} + 3.772 * Ins_0$ plus $2nd\ phase = 286 + 0.416 * Ins_{30} - 25.94 * Gluc_{30} + 0.926 * Ins_0$ ¹⁷ and the ratio

of the incremental insulin to glucose response over the first 30min during the OGTT $\frac{\Delta Insulin(30)}{\Delta Glucose(30)}$.

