12.26 Data analysis and sample size estimation

Data analysis

Statistical Analyses for primary and secondary outcomes as well as for baseline values are done in a descriptive and exploratory way.

Continuous variables will be summarized with standard descriptive statistics tables and represented graphically with displays such as box plots and histograms, and categorical variables will be described by frequency tables and standard graphical displays like bar plots. Scatterplots are used to illustrate possible correlations between the variables.

To examine differences between groups at baseline and following visits, Student's T-tests or Mann-Whitney U tests and chi-square tests will be used as appropriate. Comparisons within groups will be performed using paired T-test or Wilcoxon rank-sum test. A p-value of <0.05 is considered to indicate statistical significance, whereas appropriate correction for multiple testing like Bonferroni Correction or false discovery rate (*Benjamini and Hochberg*) will be applied. To investigate multiple relations generalized linear mixed models will be built to investigate changes between groups and over time, as the physiological changes are represented in various parameters. For high-dimensional "omics-" data appropriate multivariate modelling like Random Forests and Partial Least Squares Regression will be used to elucidate differences between groups and time-points concerning potential molecular markers regarding aging effects.

A statistical analysis plan will be prepared and finalized before database lock. All statistical analysis will be done in R (version 3.0.1.).

Sample size estimation

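### The cohort groups are matched on sex, weight and age, but the between-group tests named in 12.26 ignore the matching; the main cohort comparison should adjust for sex and age

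*Protocol*

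**What the plan says.** Protocol 10.1 sets the design of the cohort comparison: "Subjects in the ADF and control group will at least be matched by sex, weight and age". It gives no matching method, tolerance or ratio. It also still describes the earlier split ("Fifty participants of them should already practice Alternate Day Fasting", out of 100), while the synopsis gives 30 ADF and 60 control participants. That mismatch is a separate matter; here it means only that no matching ratio is fixed.

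Protocol 12.26 names the tests for group differences at baseline and later visits: "T-tests or Mann-Whitney U tests and chi-square tests will be used as appropriate". Paired tests are named only for comparisons within a group. The section adds that "generalized linear mixed models will be built to investigate changes between groups and over time", without a covariate, matching factor or matched set. It calls the analyses descriptive and exploratory, sets p < 0.05 as the significance threshold with a multiplicity correction, and promises a statistical analysis plan (SAP) before database lock.

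Two other places bear on the point. Section 8.1 lists as a primary cohort outcome "Differences in body composition (fat mass and lean body mass) between groups". Section 12.1 defines one of the insulin sensitivity indices as "ISI = 0.222 - 0.00333 * BMI - 0.0000779 * Ins_{120} - 0.000422 * age".

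**The concern.** The design uses sex, age and weight to make a self-selected group comparable with controls; the named between-group tests then set that information aside. How close the matching will be is unknown, and the tests serve neither case well.

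- **Close matching.** The groups agree on the factors, but the standard error of an unadjusted test still contains the outcome variation due to them. The interval is too wide and the test conservative.
- **Loose matching.** Whatever imbalance remains enters the estimated difference as bias, and the false-positive rate can exceed 5%.

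The mixed-model sentence does not clearly settle this. It concerns changes between groups and over time. In the cohort schedule (11.1), DXA, resting energy expenditure and intima media thickness are each listed at one visit, so those primary outcomes have no change over time to model.

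**Working it through.** **Inputs.** From the protocol: 30 versus 60 participants (synopsis); HOMA-IR mean 3, SD 1.1 and a 15% effect, read as 0.15 × 3 = 0.45 (12.26); age 35 to 65 and BMI 22 to 30 (10.3); the ISI coefficients (12.1). Assumed, because the protocol gives no value: R², and D, the imbalance left after matching in SD units of the combined prognostic index of the factors. A two-sided 5% test is also assumed.

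The protocol states no figure on this point to reproduce. Its 50 per group does not follow from the independent-samples test it names: 2 × 1.1² × (1.96 + 0.84)² / 0.45² gives 94 per group. That is a separate finding. HOMA-IR serves below only as a scale.

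**Step 1: close matching.** Unadjusted SE = 1.1 × √(1/30 + 1/60) = 0.246. Adjusted SE = 0.246 × √(1 − R²). Power for 0.45 is from the noncentral t with 86 df (group, sex and age); the unadjusted test with 88 df has 44%.

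| R² | Adjusted SE | Unadjusted SE too wide by | Adjusted 95% CI half-width | Adjusted power |
|---|---|---|---|---|
| 0 | 0.246 | 0% | 0.489 | 44% |
| 0.1 | 0.233 | 5% | 0.464 | 48% |
| 0.2 | 0.220 | 12% | 0.437 | 53% |
| 0.3 | 0.206 | 20% | 0.409 | 58% |

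**Step 2: loose matching.** Bias of the unadjusted difference = D × √R² × SD. In SE units, k = D × √R² / √(1/30 + 1/60) = D × √R² / 0.2236. If controls are drawn independently and only resemble the ADF group, type I error ≈ 1 − Φ(1.96 − k) + Φ(−1.96 − k). If each ADF subject has individually matched controls and a shift D remains, both arguments are divided by √(1 − R²).

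Example, R² = 0.3 and D = 0.4: k = 0.4 × 0.548 / 0.2236 = 0.98, and the bias is 0.4 × 0.548 × 1.1 = 0.24 HOMA-IR units.

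| R² | D | Bias (SD 1.1) | Type I error, no matched sets | Type I error, matched sets |
|---|---|---|---|---|
| 0.1 | 0 | 0 | 5.0% | 3.9% |
| 0.1 | 0.2 | 0.07 | 5.9% | 4.8% |
| 0.1 | 0.4 | 0.14 | 8.7% | 7.5% |
| 0.3 | 0 | 0 | 5.0% | 1.9% |
| 0.3 | 0.2 | 0.12 | 7.8% | 4.1% |
| 0.3 | 0.4 | 0.24 | 16.5% | 12.1% |

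Simulations with 10,000 replicates per cell and three covariates agree: at D = 0.4, 8.7% and 7.1% for R² = 0.1, and 16.2% and 12.6% for R² = 0.3. The adjusted model stayed at 4.4 to 5.5%. The formulas depend only on R² and D, so they carry over to sex and age alone when R² and D are defined for those two.

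**Step 3: what the ISI formula supports.** With BMI and age taken as uniform over the eligible ranges and the terms as uncorrelated:

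- BMI term: SD = 0.00333 × 8/√12 = 0.0077.
- Age term: SD = 0.000422 × 30/√12 = 0.0037.
- Insulin term: SD = 0.0000779 × (2-hour insulin SD), assumed as 100 to 300 formula units.

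Total SD of ISI is then 0.0115 to 0.0249. Age and BMI together explain 54% down to 12%. Age alone explains 0.0037²/0.0115² = 10% down to 0.0037²/0.0249² = 2%. The formula has no sex term.

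**Step 4: why weight is different.** Section 5 reports that "Findings from recent modified ADF studies showed 4-8% reduction in body weight after 8-12 weeks". At BMI 26 and equal height, 4 to 8% is 1.04 to 2.08 BMI points. Times 0.00333, that is 0.0035 to 0.0069 ISI units, or 0.14 to 0.60 SD of ISI (0.0035/0.0249 to 0.0069/0.0115). This is an upper bound on the ADF effect that a weight term could remove through BMI, reached only if matching left the whole weight difference in place. The bias being corrected at R² = 0.3 and D = 0.2 to 0.4 is 0.11 to 0.22 SD, so the weight term could cost more than it saves.

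**The case against.** The strongest reply is that covariate lists belong in the SAP, which 12.26 promises, and that the section also allows mixed models. In part this stands: the protocol does not say that the t-test is the sole or main cohort analysis, and a reader should not infer that it rules out modelling. But it does name unadjusted tests for group differences in a matched, non-randomised comparison, and its modelling sentence names no matching factor. This is a choice of method in the text, not merely an absent detail.

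Second, the analysis is exploratory and corrected for multiplicity. That lowers the weight of the type I error figures, but neither the label nor the correction removes bias from an estimate.

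Third, no harm is shown from the protocol's own figures. That is right as to size. With similar distributions, balanced means and no matched sets, the named test has the correct 5% level, and only precision is lost.

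Fourth, a reader might infer that matching is the only control for these factors. It is not: the limits on age and BMI in 10.3 apply to both groups and already restrict part of the imbalance.

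Fifth, a reader might infer that the model should include all three matching factors. The protocol does not support that as the main analysis. ADF participants already practise ADF, so Visit 1 weight is measured after exposure, and fat and lean mass are components of it.

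**Conclusion.** The point holds for sex and age. The unadjusted tests named in 12.26 do not use the matching in 10.1. Where sex and age predict the outcome, the interval is too wide under close matching, and residual imbalance becomes bias under loose matching. The direction follows from the design. The size rests on assumptions: for R² of 0.1 to 0.3, an SE 5 to 20% too wide under close matching; at 0.4 SD imbalance, a type I error of about 7 to 16%.

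Three stronger conclusions are not supported:

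- The named tests are not always anti-conservative. With close individual matching they are conservative (about 2 to 4%).
- The larger R² values for ISI come mostly from BMI. Age alone gives 2 to 10% under the assumptions above, and the formula says nothing about HOMA-IR or the other outcomes.
- Adjustment does not guarantee a 5% error rate. The simulated 4.4 to 5.5% assumes a correctly specified model and no unmeasured confounding, which a self-selected ADF group cannot promise. Adjustment also does not cure the small sample.

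**What to change.** In 12.26, state that the main cohort comparison for each continuous primary outcome is a linear model of the outcome (transformed if skewed) on group, sex and age, reported as an adjusted difference with its 95% CI. Keep the t, Mann-Whitney and chi-square tests as supporting summaries. Add a model that also includes weight as a sensitivity analysis, with the reason given: weight is measured after ADF exposure and contains the fat and lean mass outcomes.

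The cost is a few sentences, two degrees of freedom (86 instead of 88) and one extra model per outcome. Sex, date of birth and weight are already recorded at Visit 1 (11.2), so no data or participants are added. If sex and age predict nothing, power in the HOMA-IR illustration stays at 44%. An imbalance of 0.2 to 0.4 SD inflates the variance of the adjusted difference by 1 + (1/3)(2/3)D² = 1.009 to 1.036, which widens the SE by 0.4 to 1.8%. The main model leaves any weight imbalance that is not due to ADF unadjusted; comparing it with the weight model shows how much the result depends on that.

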4. SYNOPSIS

Study title	InterFast
Study design	Cohort study with an embedded randomized controlled pilot trial
Study participants	Healthy subjects and subjects who do already practice Alternate Day Fasting
Number of participants	90 (30 Participants in Alternate Day Fasting group and 60 participants in the control group). Those participants in the control group will be asked to participate in a short randomized controlled trial, where they will be either allocated to an Alternative Day Fasting group or another control visit.
Planned duration	18 months
Primary objective	The primary objective is to elucidate in which extent alternate day fasting influences human physiology in healthy individuals in both, the short and long term. Data of the pilot RCT will help to design a larger trial investigating Alternate Day Fasting in various groups of interest.
Secondary objectives	The secondary objective of this study is to define novel molecular markers of aging and age-related diseases.

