11.2 Visit Schedule for the cohort study

Visit 1

- Sufficient time will be provided and subjects will be encouraged to discuss all queries with the research team
- Informed consent for the study will be obtained by an investigator
- Biobank informed consent will be obtained by an investigator
- Check inclusion and exclusion criteria

- Demographics will be obtained: date of birth, gender, race, smoking status, alcohol consumption
- Weight
- Height
- Waist-Hip Ratio
- Medical history and standardized questionnaire on fertility outcomes
- Concomitant medication
- Vital signs: resting pulse and blood pressure
- Blood sampling
- ECG
- Food Frequency Questionnaire and Ferriman-Galway Score/Hamilton-Norwood Scheme
- Baseline blood tests (fasting): Full blood cell count, renal function tests, liver function tests,
- Pregnancy test in female woman of childbearing age
- Oral glucose tolerance test (OGTT)
- Application of the 24h blood pressure device
- Application of continuous glucose monitoring
- Application of accelerometer (Movisens®)

Visit 2 (9 ± 4 days after visit 1)

- Vital signs, Weight
- Physical examination
- Concomitant medication review
- Resting energy expenditure (REE)
- Measurement of endothelial function (EndoPAT 2000)
- Flow mediated dilatation (FMD)
- Blood sampling
- Oral glucose tolerance test (OGTT)
- IMT measurement
- Retinal vessel analyser
- Hand Grip Test
- Pulse wave analysis
- Echocardiography
- Collection and analysis of 24h blood pressure monitor
- Collection and analysis of accelerometer

- Removal of continuous glucose monitoring
- Dual-energy X-ray absorptiometry (DXA) and hand grip test
- Collection of sputum and faeces samples
- Buccal mucosa sampling
- Informed consent for RCT (healthy control group willing to participate in the RCT)
- Bioelectrical impedance analysis (BIA)
- Dry eye assessment (optional)

Visit 3 (2 weeks before visit 4) → only those subjects participating in the pilot RCT

- Application of continuous glucose monitoring

Visit 4 (4 weeks ± 1 week after visit 2) → only those subjects participating in the pilot RCT

- Vital signs, Weight
- Physical examination
- Concomitant medication review
- Resting energy expenditure (REE)
- Measurement of endothelial function (EndoPAT 2000)
- Flow mediated dilatation (FMD)
- Blood sampling
- Food Frequency Questionnaire
- Oral glucose tolerance test (OGTT)
- Removal of continuous glucose monitoring
- Collection of sputum and faeces samples
- Buccal mucosa sampling

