11.3 Schedule of study procedures of the pilot intervention trial

	Visit 3 (14 ± 2 days after visit 2)	Visit 4 (4 weeks ± 1 week after visit 2)	Visit 5 (2years ± 4 weeks after Visit 4)
Application of continuous glucose monitoring	X		
Concomitant medication		X	X
Vital signs		X	X
Physical examination		X	X
Blood sampling		X	X
Oral glucose tolerance test (OGTT)		X	
Continuous Glucose monitoring (CGM)		X	
Endothelial function (EndoPat 2000)		X	
Buccal mucosa sampling		X	
Saliva sampling		X	
Faeces sampling		X	
Resting energy expenditure (REE)		X	
Questionnaires (FFQ, Physical Activity)		X	X
Bioelectrical impedance analysis (BIA)		X	
Flow mediated dilatation (FMD)		X	

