Data on the effects of ADF on metabolic parameters, human physiology, aging process and molecular cellular processes in healthy subjects is very limited and a therefore an accurate sample size estimation impossible. However, we reviewed available data and used data on insulin sensitivity from a similar, albeit not entirely comparable study population with a HOMA-IR of 3 ± 1.1 (mean \pm SD)⁷. Assuming a power of 80% and a type I error rate of 5%, we would need 50 subjects per group to demonstrate an effect size of 15%, which has been demonstrated previously³⁸. Therefore the sample size of 50 subjects in the ADF and 50 subjects in the control group, as chosen for our cohort study, seems to be reasonable. In addition, previous publications have also suggested a sample size of 50 subjects per group for such types of studies with insufficient details about the outcome parameters required for a sample size estimation³⁹. Subjects in the control group will be asked to participate in a pilot, randomized controlled trial, where they are randomized to either ADF or continuing in the control group. We expect an acceptance rate of about 40%, hence a sample size of about 10 participants per group.

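### Within-group comparisons name the Wilcoxon rank-sum test, an independent-samples test, where paired data need the signed-rank test

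*Protocol*

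**What the plan says.** Section 12.26 (Data analysis) sets out the tests in two consecutive sentences. For differences between groups, at baseline and at later visits, Student's t-tests or "Mann-Whitney U tests and chi-square tests will be used as appropriate". For change inside a group: "Comparisons within groups will be performed using paired T-test or Wilcoxon rank-sum test". The signed-rank test is named nowhere in the protocol.

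The visit schedules show what a within-group comparison is in this study:

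- **RCT participants.** Resting energy expenditure, EndoPAT, flow-mediated dilatation and bioimpedance are measured at Visit 2 and again in the same people at Visit 4. Section 11.2 lists "Visit 4 (4 weeks ± 1 week after visit 2) → only those subjects participating in the pilot RCT", and the table in section 11.3 gives the same repeat visit.
- **ADF cohort group.** The table in section 11.1 has an OGTT at Visit 1 and another at Visit 2, the second marked "X (ADF group only".

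Section 12.26 calls all analyses descriptive and exploratory, applies a 0.05 threshold with a multiplicity correction, and also plans mixed models for change between groups and over time.

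**The concern.** Rank-sum and Mann-Whitney U are two names for one test, which compares two independent samples. The protocol therefore prescribes the same test for two different designs. Within one sentence it also offers the analyst a paired test (the t-test) and an unpaired one (rank-sum) for the same comparison.

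An unpaired test on paired data uses the wrong null variance. If a person's two values are positively correlated, which is usual for repeat physiological measurements, the test statistic varies less than the test assumes. Its type I error then falls below 5%, and it loses power relative to the test that uses the pairing. With negative correlation the error goes the other way. Nothing in the output would reveal the mistake: the software returns a plausible p-value. The likely harm is a missed within-arm change in pilot data that are meant to inform a larger trial.

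**Working it through.** The protocol gives no figure for the within-group tests, so there is none to reproduce. The check asks how far the named test departs from the paired one.

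**Inputs from the protocol**

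- Effect: section 12.26 says "we would need 50 subjects per group to demonstrate an effect size of 15" per cent, with HOMA-IR 3 ± 1.1. Shift = 0.15 × 3 = 0.45; in SD units 0.45 / 1.1 = 0.409.
- Pairs per RCT arm: "hence a sample size of about 10 participants per group" (40% of 50 controls = 20, in two arms = 10). With the Synopsis figure of 60 controls, 0.40 × 60 / 2 = 12.
- Pairs in the ADF cohort group: the Synopsis gives "30 Participants in Alternate Day Fasting group".
- Significance level 0.05. Sidedness is not stated; two-sided is assumed, without multiplicity adjustment.

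**Assumptions**

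- The between-visit correlation r is not in the protocol, so a range is shown.
- The 0.409 SD is stated for a contrast between groups; using it as a within-person shift is an assumption.
- Visit pairs are bivariate normal with equal variances.

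**Step 1: type I error in large samples.** With equal marginal distributions, the true variance of the rank-sum statistic is (1 − ρ_S) times the variance the test assumes, where ρ_S = (6/π) arcsin(r/2). The actual two-sided error is 2Φ(−1.96 / √(1 − ρ_S)).

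| r | ρ_S | 1.96/√(1 − ρ_S) | actual error |
|---|---|---|---|
| −0.3 | −0.288 | 1.727 | 0.084 |
| 0 | 0 | 1.960 | 0.050 |
| 0.3 | 0.288 | 2.322 | 0.020 |
| 0.5 | 0.483 | 2.725 | 0.006 |
| 0.7 | 0.683 | 3.481 | 0.0005 |

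**Step 2: simulation at the study's sizes.** Exact tests, 40,000 replicates per cell, shift 0.409 SD for power.

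| n pairs | r | rank-sum type I error | rank-sum power | signed-rank power |
|---|---|---|---|---|
| 10 | −0.3 | 0.072 | 0.153 | 0.110 |
| 10 | 0 | 0.042 | 0.117 | 0.123 |
| 10 | 0.3 | 0.021 | 0.090 | 0.161 |
| 10 | 0.5 | 0.008 | 0.066 | 0.207 |
| 10 | 0.7 | 0.002 | 0.042 | 0.310 |
| 12 | 0.3 | 0.022 | 0.106 | 0.169 |
| 12 | 0.5 | 0.009 | 0.081 | 0.222 |
| 12 | 0.7 | 0.002 | 0.052 | 0.344 |
| 30 | −0.3 | 0.080 | 0.350 | 0.260 |
| 30 | 0 | 0.049 | 0.330 | 0.325 |
| 30 | 0.3 | 0.021 | 0.304 | 0.433 |
| 30 | 0.5 | 0.008 | 0.280 | 0.568 |
| 30 | 0.7 | 0.001 | 0.240 | 0.780 |

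Signed-rank type I error stays at 0.041 to 0.050 throughout. At r = 0 the two tests are practically equal, so the loss comes from ignoring positive correlation and nothing else.

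**Step 3: robustness.** A second simulation with other routines (5,000 replicates, asymptotic rank-sum) gives, at r = 0.3/0.5/0.7:

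- n = 10: rank-sum power 0.090/0.066/0.043 against signed-rank 0.160/0.202/0.308.
- n = 30: rank-sum power 0.292/0.270/0.235 against signed-rank 0.424/0.559/0.781.

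A non-parametric test would be chosen for skewed data, so the check was repeated with lognormal values: log-SD √ln(1 + (1.1/3)²) = 0.355, a 15% reduction, same r:

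- n = 10: rank-sum power 0.108/0.085/0.059 against signed-rank 0.182/0.239/0.358.
- n = 30: rank-sum power 0.380/0.362/0.342 against signed-rank 0.503/0.639/0.848.

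**Limit on the statement.** Absolute rank-sum power does not always fall as r rises. At a shift of 1.2 SD and n = 10 it is 0.668/0.695/0.720/0.757 for r = 0/0.3/0.5/0.7, against 0.647/0.796/0.906/0.987 for signed-rank. The supported claim is the loss relative to signed-rank.

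**The case against.** The strongest reply is that this is a slip of one word. The sentence also names the paired t-test, and Mann-Whitney U has already been given to the between-group comparisons, so a different and paired test was evidently meant. The protocol also promises an SAP before database lock. That makes the modelled harm less likely, but it does not cure the text: the protocol names a specific test instead of leaving the choice open, and the wrong name can be carried forward.

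The second reply is that little depends on these tests. No legible outcome in section 8 is stated as a within-group comparison. The legible RCT primary outcomes in section 8.3 are differences between arms in change, and the mixed models can account for repeated measures. This stands, and it keeps the point minor.

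The third reply concerns the size. The effect is borrowed from a between-group assumption in a population that the protocol itself calls not entirely comparable, and every power figure depends on an assumed r. The n = 30 rows fit least well: they refer to people who already practise ADF, measured 9 ± 4 days apart, for whom no change is hypothesised. Section 11.2 also lists the Visit 2 OGTT without the ADF restriction. Those rows are therefore illustrative only. Negative correlation is unlikely for such measurements and is shown only to complete the range. In the expected case the error adds no false positives.

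**Conclusion.** The test is wrong as written; the point is minor. That the named test does not suit paired data needs no assumption. The size does: it rests on positive between-visit correlation, a borrowed shift of 0.409 SD, normal data and two-sided 5% testing.

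On those terms, with r from 0.3 to 0.7, signed-rank has about 1.8 times the power of rank-sum in an arm of 10 at the low end (0.161 / 0.090) and about 7 times at the high end (0.310 / 0.042). The correction does not rescue the arm: with 0.161 to 0.310 power, signed-rank still misses this effect in about 69% to 84% of cases. The reach is the non-parametric branch of the exploratory within-group comparisons and nothing else.

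**What to change.** In section 12.26, name the Wilcoxon signed-rank test as the alternative to the paired t-test for comparisons between visits within a group. Carry the same name into the SAP, and set paired = TRUE in the R call so that the code matches. The cost is one word in the protocol; sample size, visits and all other analyses stay as they are.
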